Document ID:	N/A	Document title:	Classification:	For internal use
		Clinical Study Protocol		
Modified:	24Jun2024		Author:	[name]
Version:	1.0		Approvers:	[name]/[name]
Status:	Final		Page:	21 of 29

Participant Accountability and Missing Data

Participants who withdraw from the study will be tabulated with the reasons for the withdrawal. A participant will only be included in the formal statistical analysis if they contribute data for both study masks.

Safety Analysis

Safety evaluations will be performed by recording adverse events at the time originally reported, and they will be followed at regular intervals until resolution or study completion, whichever comes first. Adverse events will be provided in data listings, but no statistical comparisons will be undertaken.

Interim Analysis

No formal interim analysis is planned for this study.

Exploratory Analyses

Various exploratory analyses may be performed, including subgrouping, correlation, regression, and text analytics, in order to investigate the relation between baseline factors and study endpoints. These analyses could support algorithm development or aid in future study design, but they are not required for the final study report.

Case Report Forms

Study-related case report forms (CRFs) and source documentation will be collected and maintained by the sponsor. All such documentation will be kept confidential and stored on a secure server or protected device. Only staff delegated by the PI will have the ability to enter or make changes to the CRFs and source documents.

Quality Control and Quality Assurance

The PI and study personnel will be trained to the study protocol, study product, TMF documents, monitoring plan, CRFs and/or eCRFs, direct data reporting, and all Sponsor expectations, as applicable. Once complete, training and delegations will be documented for PI and study personnel.

Data queries will be addressed by delegated study personnel, and CRF/ eCRFs will be reviewed and signed off by PI prior to study closure. Monitoring will be completed in accordance with US CFR, ICH-E6 GCP Section 6, and ISO 14155:2011 as applicable and as outlined in the monitoring plan.

Monitoring and Monitoring Plan

Onsite and/or remote monitoring will be conducted for this study. Monitoring details will be outlined in the monitoring plan.

This clinical study will be monitored by Philips (Sponsor) in compliance with the Code of Federal Regulations (CFR) for clinical research; namely, 21 CFR Parts 50, 54, 56 and 812 and others as applicable. The purpose of such monitoring is to assure that the study remains in compliance with the approved protocol, investigator agreement and regulatory requirements, to verify the

Document ID:	N/A	Document title:	Classification:	For internal use
		Clinical Study Protocol		
Modified:	24Jun2024		Author:	[name]
Version:	1.0		Approvers:	[name]/[name]
Status:	Final		Page:	22 of 29

completeness, reliability and accuracy of study data and to resolve any issues that arise during the conduction of the study. The Sponsor will conduct monitoring visits as specified by the monitoring plan. Monitoring will be conducted by trained clinical research professionals.

It has been determined that this study does not require a Data Safety Monitoring Board (DSMB).

Data Management System

All data will be entered into a 21 CFR Part 11-compliant electronic data capture system (EDC) provided by the Sponsor. The data will be housed within a secure server and accessible only to the sponsor, study personnel, and investigators. Access to the EDC system will be secured through logins managed by a system administrator and appropriate training will be provided. The EDC system provides the capability to perform data management activities within a consistent, auditable, and integrated electronic environment (data security, data entry, data validation). Data entries and modifications will be recorded via an audit trail. If the data manager or study monitors identify data errors or inconsistencies, they will generate queries that will be sent to the Principal Investigators and study staff. After queries are resolved, the database will be locked, and the data will be imported into statistical software and analyzed by biostatisticians.

Deidentified patient data will be retrieved from Care Orchestrator after participants have completed both study arms. Raw data files will be provided to the study team and housed within a server where they will be accessible by the sponsor, study personnel, and investigators.

Protocol Deviations

A protocol deviation is defined as the instance of failure to follow, intentionally or unintentionally, the requirements of the protocol. The noncompliance may be either on the part of the participant, the investigator, or research staff. The PI or designee shall document and explain any deviation from the approved protocol that occurs during the course of the study. These deviations may be major or minor/administrative in nature. Please see the table below for description and reporting requirements for each type. Protocol deviations will be reported to IRB per their policy, by the site or Sponsor, as applicable.

Type	Description	Reporting Requirements
Minor Deviation	Deviation does not have a significant effect on subject safety/rights or the scientific soundness of the study plan	Document on appropriate CRF

Document ID:	N/A	Document title:	Classification:	For internal use
		Clinical Study Protocol		
Modified:	24Jun2024		Author:	[name]
Version:	1.0		Approvers:	[name]/[name]
Status:	Final		Page:	23 of 29

Major Deviation	Deviation does have a significant effect on subject safety/rights and/or the scientific soundness of the study plan, or significantly impact the integrity of research data	Document on appropriate CRF and report to sponsor within 7 calendar days from site awareness.
-----------------	---	---

Ethics

The IRB for this study is the Allendale Institutional Review Board, [name]; [contact].

Privacy rules and requirements according to governing regulations will be implemented. All the information collected as part of this study will be kept confidential. All information collected for this study will be kept in a secured area or stored in a password protected computer if digital. Except when required by law, participants will not be identified by name, address, telephone number, or any other direct personal identifier in study records. For records disclosed outside Sponsor, participants will be assigned a unique code number. The key to the code will be kept by the investigator. Data will be managed by study number and analyzed anonymously.

A unique source record will be created for each study participant. Privacy rules and requirements according to federal and state governing regulations will be implemented. The study record will include documentation of the informed consent form review process, HIPAA completion according to site policies, and applicable medical history. The Sponsor will have access to these source records.

Study data and source will be made available for study related monitoring or audits by the IRB/IEC, sponsor, or regulatory inspection(s).

The data collected during this study may be reanalyzed at a later date and may be combined with the results of other studies. Philips and third parties approved by Philips may use the results of this study for other research and commercial purposes, including:

- Reviewing the safety or effectiveness of the study device and other products or therapies
- Evaluating other products or therapies for patients
- Developing a better understanding of disease
- Identifying trends within the data

Results of the study related data, medical and sleep history, information obtained from surveys and device data will be reported and received by Philips. Philips will use participant study data for research purposes to support scientific and marketing objectives described in this protocol.

In addition, participant records may be reviewed in order to meet federal and state regulations. Reviewers may include representatives from the FDA, other government authorities, Philips, and the Institutional Review Board (IRB) to gather information related to the study. By signing the associated informed consent, participants grant permission for these parties to review their

Document ID:	N/A	Document title:	Classification:	For internal use
		Clinical Study Protocol		
Modified:	24Jun2024		Author:	[name]
Version:	1.0		Approvers:	[name]/[name]
Status:	Final		Page:	24 of 29

confidential information. Philips will ensure that it follows all applicable state and federal data protection regulations.

Data Handling and Recordkeeping

Hard copies of study documents, if required, will be kept on site for at least two years after study completion. Only approved study staff will be granted access to the data directly entered into the EDC. The sponsor will maintain study records until the study product's end of life (EOL) + 15 years and biometric data for 15 years. Records will be stored at Iron Mountain, a secure information management services company.

Risk and Benefit Analysis

Philips has determined that participation in this study poses minimal risk. It is the opinion of the Sponsor and the PI that the benefits of this protocol outweigh the risks. Both masks being used in the study have been cleared for marketing by the US FDA.

Anticipated Clinical Benefits

Participation in this trial will not result in direct benefit to the participant.

Anticipated Adverse Device Effects

Overall, the risks in this study are minimal and not expected to be different from those encountered by patients prescribed PAP therapy outside of research; however, potential risks are listed below, and they will be described in the ICF and will be repeated verbally to the participants during the consenting process.

Possible risks or effects from use of the products in this research study include, but are not limited to:

- The presence of redness, marks, indentations and/or pressure wherever the mask or headgear touches the face.
- Skin irritation, skin breakdown, bruising or blisters where the mask or headgear comes in contact with the face.
- Discomfort or irritation (itchiness, excessive tearing, burning, dryness, puffiness, infection, blurred vision) of the eyes.
- Eye pain.
- Dry mouth or upper airway.
- Nasal irritation, a feeling of a dry nose, nose bleeds or excessive running of the nose.
- Stomach distension, belching.
- Claustrophobia.
- The study mask may deliver airflow differently from what the participant is accustomed to, and as such, breathing may feel more difficult than what they would experience with a different mask.
- Unusual chest discomfort, breathing discomfort, or shortness of breath.
- Headaches or increased drowsiness.
- In rare cases, the mask may cause tooth, gum, or jaw soreness or aggravate an existing dental condition.
- Pressure or pain in the ears.

Document ID:	N/A	Document title:	Classification:	For internal use
		Clinical Study Protocol		
Modified:	24Jun2024		Author:	[name]
Version:	1.0		Approvers:	[name]/[name]
Status:	Final		Page:	25 of 29

- The participant's condition may not improve or may worsen while participating in this study.

Careful mask application, sizing, and adjustment should address or correct mask-related issues. Participants should be instructed to avoid overtightening the headgear and to only use the mask when the device is on and blowing air to avoid rebreathing exhaled air and potential suffocation. Note that some rebreathing may occur at low pressures. Breathing discomfort should be transient or can be addressed with counseling. However, all of these complications are normally encountered while using PAP therapies, and there should be no additional risk from participating in this study given that participants will be recruited on the basis of being established on therapy.

If a participant reports they have experienced an adverse event, they will be directed to contact the site study staff and instructed to discontinue therapy if appropriate.

Participation Risk:

- The loss of confidentiality is a potential risk of being in the study, but the site and sponsor will do everything to make sure that participant information is protected.
- Participants may experience frustration, fatigue, and anxiety while completing the study activities.

There may be a possibility of unanticipated or unknown risks; however, for this activity Philips has determined that this risk is low.

Publication and Registration

This study will be registered on ClinicalTrials.gov. There may be plans to publish the results of this trial, beyond the use of the data in marketing materials.

Document ID:	N/A	Document title:	Classification:	For internal use
		Clinical Study Protocol		
Modified:	24Jun2024		Author:	[name]
Version:	1.0		Approvers:	[name]/[name]
Status:	Final		Page:	26 of 29

References

2. Adult Obstructive Sleep Apnea Task Force of the American Academy of Sleep Medicine. Clinical Guideline for the Evaluation, Management and Long-term Care of Obstructive Sleep Apnea in Adults. *Journal of Clinical Sleep Medicine*. 2009;05(03):263-276. doi:10.5664/jcsm.27497

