		Clinical Study Protocol		
Modified:	24Jun2024		Author:	[name]
Version:	1.0		Approvers:	[name]/[name]
Status:	Final		Page:	9 of 29

		
Proportion of patients who prefer the Amara View compared to the AirFit F40 for the following:
 
 • Seal • Comfort • Stability • Noise level • Headgear • Mask cushion attachment ease of use • Less disruptive air venting • Overall preference
Secondary Objective: compare residual AHI values between the Amara View and AirFit F40 masks during PAP therapy.	Residual AHI values will tend not to differ between the Amara View and AirFit F40 masks.	Residual AHI recorded by the participants PAP device while using the Amara View and AirFit F40 masks
Secondary Objective: compare the recorded leak values between the Amara View and ResMed AirFit F40 masks during PAP therapy.	Leak values will tend to be lower for the Amara View mask compared to the AirFit F40 masks.	Leak recorded by the participants PAP device while using the Amara View and AirFit F40 masks.
Secondary Objective: compare the air pressure used during PAP therapy between the Amara View and AirFit F40 masks	Air pressure values will tend not to differ between the Amara View and AirFit F40 masks	Air pressure (cmH20) used during PAP therapy recorded by the participants' PAP device while using the Amara View and AirFit F40 masks
Secondary Objective: compare the adherence to PAP therapy while using the Amara View and AirFit F40 masks	Adherence to PAP will tend not to differ when using the Amara View mask compared to the AirFit F40 mask	Daily hours of use of PAP therapy recorded by the participants' PAP device while using the Amara View and AirFit F40 masks

Data obtained as part of the secondary objectives from this protocol will be used as part of a Post Market Clinical Follow-up Activity.

Document ID:	N/A	Document title:	Classification:	For internal use
		Clinical Study Protocol		
Modified:	24Jun2024		Author:	[name]
Version:	1.0		Approvers:	[name]/[name]
Status:	Final		Page:	10 of 29

Study Design

This is an open-label, randomized cross over trial, comparing patient feedback between the Amara View MCFFM and the AirFit F40 MCFFM. This study will recruit approximately 40 adult patients who are established on PAP or Bi-Level therapy at the time of enrollment.

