After the first 15-day trial period with the first study mask, participants will return to the site for their second study visit. Participants will be instructed to bring their PAP device and return the first study mask to the visit.

Participants will complete a mask attributes survey on the first study mask and then they will be fitted with the second study mask. Fitting procedures will follow the same procedure as described above in the baseline visit. After the mask fitting, participants will be given the second study mask to take home and provided with the Instructions for Use. They will be encouraged to use the mask for the full 15 days of the second trial period. Participants will be instructed to contact the site if they have issues with the recommended cushion and/or headgear size as needed.

If participants did not return the first study mask at the second study visit, they will be asked to bring it to the third study visit.

Document ID:	N/A	Document title:	Classification:	For internal use
		Clinical Study Protocol		
Modified:	24Jun2024		Author:	[name]
Version:	1.0		Approvers:	[name]/[name]
Status:	Final		Page:	12 of 29

It is anticipated the survey completion and mask fitting will take approximately 60 minutes to complete.

Visit 3

After the second 15-day trial period with the second study mask, participants will return to the site for the third and final study visit. During this visit, participants will complete a mask-attributes survey on the second study mask and return all study product.

It is anticipated the survey completion and study product return will take approximately 30 minutes to complete.

After participants have completed both study arms, deidentified data from participants' PAP devices will be extracted from the connected device software Care Orchestrator (CO) for Philips device users only. The site coordinator will confirm the data has been uploaded into CO at visits 2 and 3.

Unscheduled Phone Calls

Documentation of unscheduled phone calls will be captured within the EDC.

Conclusion of Participation

Once the participant returns the study mask(s) and completes the survey, their participation in the study will be complete. Participants will be active in the study for approximately 30 days but no more than 60 days after receipt of the first study mask.

Participant Reimbursement

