 - DreamStation Go CPAP, APAP or Auto CPAP
 - Dorma 400 or 500 CPAP or Auto CPAP
 - System One ASV4
 - System One (Q-Series) 50 series CPAP, Auto CPAP, or BiPAP
 - System One (Q-Series) 60 series CPAP, Auto CPAP, or BiPAP
 - C Series ASV, S/T, or AVAPS
 - REMStar SE Auto CPAP

Withdrawal

The term 'discontinuation' refers to the participant's premature withdrawal from the study prior to completing all procedures. Participants may be discontinued from the study for any of the following reasons:

- At the discretion of the PI or his designee, if he believes that continuing with the protocol is not in the best interest or may prove harmful to the participant. Such a decision may be precipitated by adverse events, including fever, nausea, rash, changes in vital signs, or the development of a new medical condition. The investigator will be responsible for making medical/safety decisions regarding the participants continuing in the study.
- At the request of the participant for any reason (or none)
- At the request of the sponsor

Document ID:	N/A	Document title:	Classification:	For internal use
		Clinical Study Protocol		
Modified:	24Jun2024		Author:	[name]
Version:	1.0		Approvers:	[name]/[name]
Status:	Final		Page:	17 of 29

- Non-compliance, as defined by failure to respond to phone and/or email contact after three attempts made by a study representative or failure to attend study appointment(s) (lost to follow-up), or being unwilling/unable to consistently use PAP (at least 4 days per week) along with the provided mask
- If the study mask/s provided is/are found to be inadequate for use (e.g., seal, stability, comfort, air flow, etc.)
- If eligibility status changes during the study and the participant no longer meets inclusion or exclusion criteria

The study team will document whether or not each participant completed the study. If, for any participant, study treatment or assessments were discontinued, the reason will be recorded. No further data will be collected following study withdrawal. Each patient's health care provider will be responsible for follow-up care following study withdrawal with communication from research staff.

Participants may withdraw from the study at any time. Withdrawal from the study will not affect their medical treatment or future participation in a research study.

Treatment of Subjects

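### The paired adherence comparison can lose participants because of low use with a mask, so unequal mask-related withdrawal would pull it toward the hypothesised absence of a difference

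*Combined protocol and SAP*

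**What the plan says.** The Study Objectives table sets a secondary objective on adherence, measured as daily hours of use recorded by the PAP device with each mask. Its hypothesis is "Adherence to PAP will tend not to differ when using the Amara View mask compared to the AirFit F40 mask". No equivalence margin is given. The same section says that the secondary data will feed a post-market clinical follow-up activity.

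The Withdrawal section lists reasons for which a participant may be discontinued. Two of them concern the mask: "being unwilling/unable to consistently use PAP (at least 4 days per week) along with the provided mask" and "If the study mask/s provided is/are found to be inadequate for use (e.g., seal, stability, comfort, air flow, etc". It adds: "No further data will be collected following study withdrawal".

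Statistical Analyses applies the paired difference (Amara View minus AirFit F40) to adherence. Participant Accountability and Missing Data states: "A participant will only be included in the formal statistical analysis if they contribute data for both study masks". It also states: "Participants who withdraw from the study will be tabulated with the reasons for the withdrawal". The tabulation is not said to be by mask.

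Two places deal with device data. The Visit 3 text begins "After participants have completed both study arms, deidentified data" and limits extraction to Philips device users. Data Management System says: "Deidentified patient data will be retrieved from Care Orchestrator after participants have completed both study arms".

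**The concern.** Low use with a mask is both a value of the adherence outcome and a permitted reason to leave the study. A participant withdrawn in the first period never receives the second mask and cannot form a pair. One withdrawn in the second period has data on both masks, but is also lost if the two retrieval statements are read as limiting retrieval to those who completed both arms.

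The paired difference then describes people who tolerated both masks. If one mask is abandoned more often than the other, that difference in use is partly or wholly removed from the estimate, which moves toward the stated hypothesis. This is a shift in the estimate, so the plan's emphasis on effect sizes and confidence intervals does not correct it. A larger sample would narrow the interval around the shifted value. What is at stake is a statement that adherence does not differ, carried into post-market follow-up.

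**Working it through.** **Inputs from the protocol.** About 40 enrolled and about 30 expected to complete (Number of Subjects), so the implied loss is 1 - 30/40 = 25%, or 10 people. There is no power calculation to reproduce (Determination of Sample Size). The low-use threshold is 4 days per week (Withdrawal). Entry requires at least 4 h/night on at least 4 days per week (Inclusion Criteria).

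**Not in the protocol, so assumed.** The reasons for the 10 losses, their split between masks, the number of Philips device users, the SD of paired differences, and the hours lost by someone who does not tolerate a mask (h). Three values of h are used:
- 4 h/day: 4 h every night falling to none.
- 4 × (7 - 3)/7 = 2.29 h/day: 4 h on 7 nights falling to 4 h on 3 nights. The entry minimum falling to none gives the same figure, 16/7.
- 4 × (4 - 3)/7 = 0.57 h/day: 4 nights falling to 3, the smallest crossing of the threshold.

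**Step 1: ceiling on what can be hidden.** Suppose completers show no difference, and a and b participants are lost on the two masks. The hidden difference is (a - b)/40 × h. If all 10 losses are mask-related:

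| Split | h = 4 | h = 2.29 | h = 0.57 |
|---|---|---|---|
| 10-0 | 1.00 h | 0.57 h | 0.14 h |
| 8-2 | 0.60 h | 0.34 h | 0.09 h |
| 5-5 | 0 | 0 | 0 |

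The zero difference in completers is an input here, not a result.

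**Step 2: withdrawal is discretionary.** Let intolerance be pA = 20% on Amara View and pF = 5% on AirFit F40, independent. Let r be the share of intolerant participants who are withdrawn. The true difference is -(pA - pF) × h. The expected paired difference in those retained is

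-h × [pA(1 - r)/(1 - r·pA) - pF(1 - r)/(1 - r·pF)].

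For h = 4 and r = 0.5: -4 × (0.10/0.90 - 0.025/0.975) = -0.34 h, against a true -0.60 h. For r = 0.25: -4 × (0.15/0.95 - 0.0375/0.9875) = -0.48 h.

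Coverage of the 95% t interval was simulated (60,000 trials per row) with 20 enrolled device users and an SD of 1.0 h for paired differences among tolerators:

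| h | True difference | Share withdrawn | Estimate | Mean pairs | Coverage of true value |
|---|---|---|---|---|---|
| 4 | -0.60 | all | 0.00 | 15.2 | 42% |
| 4 | -0.60 | half | -0.34 | 17.5 | 86% |
| 4 | -0.60 | quarter | -0.48 | 18.8 | 93% |
| 2.29 | -0.34 | all | 0.00 | 15.2 | 76% |
| 2.29 | -0.34 | half | -0.20 | 17.5 | 92% |
| 0.57 | -0.09 | all | 0.00 | 15.2 | 94% |

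In the first row the mean CI half-width is 0.54 h and the result is non-significant in 95% of trials.

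**Step 3: sensitivity, full withdrawal and h = 4.** With 13, 27 or 40 device users enrolled, coverage is 61%, 27% or 11%. With 20 enrolled and an SD of 0.5 or 1.5 h, it is 1% or 69%. With intolerance of 15% against 10% (true -0.20 h), it is 89%. With equal intolerance it is 95% and there is no bias.

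**Step 4: the two readings of retrieval.** Suppose second-period withdrawals do contribute and every first-period intolerant participant is withdrawn. Those starting on Amara View then show +4 × 0.05 = +0.20 h with 80% retained. Those starting on AirFit F40 show -4 × 0.20 = -0.80 h with 95% retained. With equal numbers in each order the average is (0.80 × 0.20 - 0.95 × 0.80)/1.75 = -0.34 h. The milder reading therefore still loses part of the difference, about as much as the half-withdrawal row.

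**The case against.** A reader might infer that Stopping Rules, which says no individual discontinuation rules are specified, contradicts the Withdrawal list. It does not: its next sentence allows case-by-case withdrawal by investigators and points forward to that list. Absence of a fixed rule and a list of discretionary grounds are compatible.

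A reader might also infer that the comparison is bound to return zero. The text does not support that. Withdrawal is optional, and once only half of intolerant participants are removed, more than half of the difference remains visible. The ground is stated in days per week while the endpoint is hours per day, so short nights on 4 or more days stay in the data. No visit is scheduled between Day 15 and Day 30, so low use in the second period may not be acted on before Visit 3, when both arms are complete.

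The loss of second-period withdrawals rests on one reading. The retrieval statements can be taken as giving timing only. Upload is confirmed at Visit 2 as well as Visit 3, and the bar on data after withdrawal does not exclude nights recorded before it.

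Finally, the study is declared unpowered and aimed at directional trends, the hypothesis makes no formal equivalence claim, and nothing in the plan treats a non-significant p-value as proof of no difference. Reasons for early termination are also listed under Participant Disposition. All of this stands and limits the point. It does not remove it: first-period withdrawals cannot form a pair on any reading, and neither the listing nor the tabulation enters the adherence estimate or is stated to be by mask.

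**Conclusion.** The concern holds in conditional form. The plan lets low use with a mask remove a participant from the comparison of use between masks. If mask-related withdrawal is unequal, the paired difference moves toward the hypothesised result; if it is balanced, it does not. The documents do not allow the size to be stated. Under the assumptions above it runs from negligible (0.57 h/day lost, or balanced withdrawal) to the whole of a 0.60 h/day difference (4 h/day lost, 20% against 5% intolerance, every intolerant participant withdrawn), with partial removal in between. This affects how a secondary result may be interpreted; it is not an error in a confirmatory test. It should still be changed, because the result is to be used beyond design feedback and the change is cheap.

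**What to change.** No change to the withdrawal grounds is proposed.

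1. Visit 3 and Data Management System: state that device data are retrieved for every Philips-device participant after completion or withdrawal, covering nights up to the withdrawal date.
2. Statistical Analyses and Participant Accountability and Missing Data, adherence only: keep the paired difference, labelled as participants who used both masks. Add a sensitivity analysis of all mask periods with device data, including those of withdrawn participants, in a mixed model with mask, period and participant. Average hours per day from dispensing of that mask to the earliest of the visit ending the period, dispensing of the next mask, or withdrawal. Mask return must not be the end point: the first mask may come back at Visit 3 or later, and second-mask nights would then enter the first-mask average. Counting days after the mask is stopped as 0 h is optional. If done, label it a different quantity from hours while using the mask, because PAP therapy continues throughout the trial (Treatment of Subjects).
3. Participant Accountability and Missing Data: tabulate withdrawals for low use or mask inadequacy by the mask in use, with exact binomial CIs, beside the adherence result.
4. Report the estimate, 95% CI and number of Philips-device pairs, and state that p ≥ 0.05 will not be presented as evidence of no difference.

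The cost is wording, one model and one table, with no extra participants, visits or data after withdrawal. The model is only a partial remedy. In a 500-trial simulation with full withdrawal in the period of intolerance (between-person SD 1.5 h, within-period SD 0.71 h, 20 enrolled), it recovered -0.40 of -0.60 h and -0.21 of -0.34 h, roughly two-thirds. Coverage was 88-91% across 20 and 40 enrolled, with a wider CI than the paired analysis. The by-mask withdrawal count must therefore accompany it.
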